- Adverse events and deviations are reported to IRB per current guidelines
- All versions of the IRB protocols and informed consent forms are electronically archived
- Reporting all protocol deviations (exceptions and violations) are reported to IRB as required.

Informed Consent

- Ensure that participant identification is on all pages of the ICF
- There is documentation that the participant is given a copy of the consent form
- The participant and study representative signed and dated the consent form for him/herself.
- The participant initialed and dated all appropriate pages on the informed consent form.
- Note to file made for any informed consent deviations.
- Ensure a valid (current version date) copy of the consent form was used
- Contact information collected on study participant and two additional study contacts.

Protocol:

- Confirm that the study staff is conducting the study in compliance with the protocol approved by IRB and if applicable, FDA.
- The protocol deviations (exceptions and violations) are documented appropriately and reported to IRB as required.

Electronic Case Report Forms:

- Review participant files to ensure that accuracy, and completeness of the data
- Any correction made to the eCRFs is automatically dated in REDCap. The original entry is archived and hard copies can be printed.
- Note files made for missing or incomplete data and to explain any discrepancies or additional comments in appropriate text fields.

Other documents:

- CVs for all study staff are on file and updated every 2 years
- Medical licenses for the PIs and Co-Investigators are on file and updated prior to expiration
- Yearly financial disclosures for PIs and consultants

18c. Clinical Monitoring

No clinical monitoring will take place in this study as it is a single site trial.

18d. Reports

Reports as outlined in the communications plan above will be prepared to keep the study staff up to date and engaged, as well as help to check quality control. These reports will take the form of:

- Weekly status emails to the PI by the research assistants and study coordinator
- Data and safety monitoring reports prepared by the study investigator and other staff to be reported to the Safety Officer, DSMB, and the UAB IRB as requested.
- Monthly reports that will be compiled by the research assistant and staff statistician in presentation form for study meetings will include
 - Target and actual enrollment,
 - Individuals screened with reasons for screen failure,
 - Enrollment status (enrolled, active, completed, discontinued treatment, and lost to follow-up).
 - Electronic forms completed and entered
 - Missing or erroneous data.
 - AEs and SAEs

19. Study Closeout

At the conclusion of the study the following procedures will be done to verify all study related obligations have been met. Verification that all study procedures have been completed including, but not limited to the following procedures include:

- All data has been collected
- All data queries have been completed.
- All electronic source materials have been properly documented and archived
- Any study related supplies and unused medication is returned for destruction.
- Assurance that correspondence and study files are accessible for audits.
- Reminder to investigators of their ongoing responsibility to maintain study records and to report any relevant study information to the KAI.
- IRB notification of the study completion and stored copy of the notification.
- Preparation of a report summarizing the study's conduct and results.
- Participant notification of the study completion.

20. Policies

All staff will be instructed in their study specific responsibilities regarding data safety and confidentiality. Additionally all staff will be cautioned against the release of data to any unauthorized individuals and no data will be released to any individual without first obtaining approval from NIAMS and/or the UAB IRB.

This section of the PROTOCOL will discuss the safeguards which have been put in place by the PIs to ensure participant confidentiality and data security.

The following is a list of study participant confidentiality safeguards:

- Data flow procedures – As this is a single site study and therefore no data identifying participants will be transmitted between sites. The study statistician and coordinator will provide thorough data entry and confidentiality training to all staff involved in data collection and data entry. All eCRFs and copies will be included in participant electronic study binder on day of visit or phone check in. The study statistician, project manager, and coordinator will review all data collected weekly to ensure all forms are being completed correctly in REDCap and are intact. No data will leave the site, as this is a single site study, so no other data flow will occur.
- Electronic files – All data identifying participants will be stored electronically will be maintained by the study statistician and will be maintained behind the UAB firewall.
- Data listings – Data or information containing the participant name, study ID, medical information, record number, Social Security Number, or any other unique identifier will under no circumstances be included in any published data listing.
- Data distribution - data listings that contain participant name, name code, or other identifiers easily associated with a specific participant will not be distributed.
- Data disposal - computer listings that contain participant-identifying information should be disposed of in an appropriate manner.
- Access - participant records stored in the data center should not be accessible to persons outside the center without the express written consent of the participant.
- Storage – All data collected during this will be stored on UAB Department of Medicine Servers. No data will leave the site, as this is a single site study, so no other data flow will occur. Any printed study forms and related documents created both during and after study completion will be stored in a secure location in UAB Faculty Office Tower.
- Passwords – Each study related file will be password protected. Additionally, limitations will be placed on general access to the study's REDCap system and to the functions that individuals can use. All passwords will be changed on a regular basis.
- User Training - Study staff with access to clinical computer systems will be trained in their use with an emphasis on, and the importance of, system security.
- System Testing - Prior to the use of the Redcap system, and subsequent to any modifications, the system will be tested to verify that it performs as expected. Testing will verify that the password-activated access system performs as intended.
- System Backups - Backup copies of electronic data will be made by the study coordinator or study statistician.

21. Publications

Upon completion of the study we will publish our findings in peer reviewed journals.

Authors must participate in the writing of the paper in accordance with the International Committee of Medical Journal Editors guidelines (N Engl J Med 1991;324:424-8). First authors are expected to delete names from the final list of authors if those individuals have not satisfied criteria for authorship in accordance with those guidelines. The first author on proposed or active writing projects will be decided on by the project's Publication Working Group. The project's Publication Working Group will develop a listing of first (lead), second and senior (last) author for all potential reports. In general, the researcher who first conceived of the project and submitted a plan for the manuscript should have the option of serving as first author. Conflicts in first authorship should be resolved by all members of the Publication Working Group. In the event that the Publication Working Group is unable to resolve a conflict, the UAB CORT Executive Committee will adjudicate and may assign the first authorship.

All project manuscripts must be approved by the Publication Work Group prior to submission to journal or presentation. The UAB CORT Executive Committee will assist in the review of all manuscripts or scientific presentations with the goal to ensure their content and face validity.

UAB CORT project investigators are required to inform and submit copies to the UAB CORT Executive Committee of all abstracts, posters, presentations, slides and manuscripts. It is the responsibility of the first (lead) author to ensure that appropriate journal submission procedure is adhered to. Any substantial changes to an approved manuscript prior to publication whether required by the journal or not, must be discussed with the co-authors. The co-authors should receive the proposed re-submissions at least 1 week prior to the journal re-submission.

22. Protocol Maintenance

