Women will need to be evaluated between days 1-7 of their menstrual cycles for study visits. This will be done to make FMD results comparable among women, and between women and men, since hormone levels have been shown to affect FMD results.⁷⁵ Participants will be entered into the trial and will be randomized to receive allopurinol or placebo. Neither the participant nor the Principal Investigator will know the drug assignment. This will begin Phase 1 (i.e., the first four weeks of the intervention). Randomization lists, stratified by race and gender, will be generated using a random number generator prior to the initiation of the study (i.e., in the first six months of study funding). Randomization will occur in blocks of size 2, 4, or 8 and will be stratified on sex and race/ethnicity to ensure order of treatment administration is balanced by sex and race. Randomization will occur using a random number generator. The sequence of treatment assignment will be determined by the random number generator and held by the pharmacist creating treatment arm study pill over-encapsulation. The pharmacist will maintain the master list and securely store the randomization files.

Visit 2:

- Blood pressure
- Updated medical history
- Blood sample
- Urine sample
- 24-hr ABPM
- FMD
- CBC
- Liver tests-Liver tests are alanine aminotransferase, aspartate aminotransferase, and alkaline phosphatase
- Serum creatinine
- Serum urate
- hsCRP
- Serum banking
- Pregnancy test†
- Cotinine test
- Pill count from run-in
- Potential adverse events
 - Assess any gastrointestinal symptoms, rash, or any other untoward effect
 - If potential untoward effect, study investigator will follow-up with subject

- Dispense 4 week course of allopurinol or placebo based on treatment assignment following return of the ABPM monitor

Interim visit check-in:

Between study visits, there will be four contact check-ins to encourage study compliance. These will be made by the study coordinator or research assistant. Additionally the study coordinator and/or research associate will assess the following during the call.

- Pill count
- Potential adverse events
 - Assess any gastrointestinal symptoms, rash, or any other untoward effect
 - If potential untoward effect, study investigator will follow-up with subject
 - If no untoward effects, subject will be encouraged to continue medication

Visit 3:

- Blood pressure
- Physical exam (head/neck/heart/abdomen)
- Updated medical history
- 24-hr ABPM
- FMD

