- Blood sample
- Urine sample
- CBC
- Liver tests-Liver tests are alanine aminotransferase, aspartate aminotransferase, and alkaline phosphatase
- Serum creatinine
- Serum urate
- hsCRP
- Serum banking
- Pregnancy test†
- Cotinine test
- Pill count
- Potential adverse events
 - Assess any gastrointestinal symptoms, rash, or any other untoward effect
 - If potential untoward effect, study investigator will follow-up with subject

Following Visit 3, participants will begin a “wash-out period” before crossing over to the alternate treatment assignment. The wash-out period will last one month. Allopurinol has a half-life of 1-2 hours before being converted to oxypurinol, which has a half-life of 18 to 30 hours. ² Thus, thirty days from the last allopurinol

dose is an adequate wash-out period and no persistent effects from the drug should be expected at this point. In fact, a subsequent amendment to the protocol (approved by IRB on August 2016) allowed the duration of washout for male participants and some female participants without a regular menstrual cycle (e.g., hysterectomy) to be shortened to 2 weeks. This approach is supported by interventional studies by our co-Investigator [REDACTED] and others investigating the effect of allopurinol on cardiovascular disease. Additionally during the washout period we will continue our phone check-ins with participants. These phone calls will be made by the study coordinator or research assistant, will take about 10-15 minutes each, and will assess any potential adverse events the participants may be experiencing.

Visit 4

- Blood pressure
- Physical exam (head/neck/heart/abdomen)
- Updated medical history
- Blood sample
- Urine sample
- 24-hr ABPM
- FMD
- CBC
- Liver tests-Liver tests are alanine aminotransferase, aspartate aminotransferase, and alkaline phosphatase
- Serum creatinine
- Serum urate
- hsCRP
- Serum banking
- Pregnancy test†
- Cotinine test
- Potential adverse events
 - Assess any gastrointestinal symptoms, rash, or any other untoward effect
 - If potential untoward effect, study investigator will follow-up with subject
- Dispense 4 week course of allopurinol or placebo based on treatment assignment following return of the ABPM monitor

Interim visit phone call-in :

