Between study visits, there will be four follow-up phone calls to encourage study compliance. These phone calls will be made by the study coordinator or research assistant and will take about 10-15 minutes each. Additionally the study coordinator and/or research associate will assess the following during the call.

- Pill count

- Potential adverse events
 - Assess any gastrointestinal symptoms, rash, or any other untoward effect
 - If potential untoward effect, study investigator will follow-up with subject
 - If no untoward effects, subject will be encouraged to continue medication

Visit 5:

- Blood pressure
- Updated medical history
- Blood sample
- Urine sample
- 24-hr ABPM
- FMD
- CBC
- Liver tests-Liver tests are alanine aminotransferase, aspartate aminotransferase, and alkaline phosphatase
- Serum creatinine
- Serum urate
- hsCRP
- Serum banking
- Pregnancy test†
- Cotinine test
- Pill count
- Potential adverse events
 - Assess any gastrointestinal symptoms, rash, or any other untoward effect
 - If potential untoward effect, study investigator will follow-up with subject

24-hour Ambulatory Blood Pressure Measurements (ABPM)

All patients had 24-hour ABPM evaluations with an automated, noninvasive, oscillometric device (Spacelabs Healthcare, Inc., [name], U.S.A). An appropriate sized cuff is used with a cuff bladder encircling at least 80% of the arm, according to guidelines.³⁷ Participants will be receive careful instructions at each visit about the appropriate use of the device, including a handout that contains information about error codes that may occur and possible ways to resolve them. They will be asked to wear the device as much as possible within the 24 hour recording period. Participants will be encouraged to contact study staff immediately should they not any abnormalities in cuff or monitor function (e.g., cuff failure to inflate fully, repeat error codes). The first measurement will be obtained at the end of the clinic visit to ensure proper fit and function. ABPM monitors will be outfitted with new AA batteries for each participant and will

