be programmed to obtain blood pressure recordings every 20 minutes for the daytime (awake) and every 30 minutes for the nighttime (asleep) for a 24-hour period. For the purposes of this study, daytime will be defined as 06:00-21:59 and nighttime will be defined as 22:00-05:59. Compliant 24-hour ABPM will be defined as a minimum of 14 successful daytime recordings and 5 nighttime readings. Those with less than these minimal thresholds will be asked to repeat the test. Should a non-compliant ABPM be unattainable, missing data will be handled with multiple imputation analysis. Normal ABP is defined as mean 24-hour BP <130/80 mmHg with a daytime (awake) BP of <135/80 mmHg and a nighttime (asleep) BP of <120/70 mmHg by ABPM according to guidelines.^{36,37} Average ABPM will be weighted for the proportion of daytime and nighttime blood pressure readings. At the time of data analysis, manual readings will be discarded when there is a concurrent automated reading within the same 5-minute period. In instances where the ABPM was recorded outside of the appropriate time (e.g., the participant did not follow instructions as to the timing of the test), each ABPM will be evaluated by two data analysts blinded to condition to determine

Flow-Mediated Dilatation analyses (FMD)

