All study investigators and participating coordinators will be blinded to treatment assignment. If there is a serious adverse event, then unblinding will be discussed and if deemed necessary to unblind the participant, then the ID of the unblinded participant, reasons for unblinding, name of the pharmacist and a list of whomever becomes unblinded will be kept in the study binder. The pharmacist will contact that participant's primary physician about the exposure. If necessary, the participant will be withdrawn from the study. The pharmacist will hold the randomization codes securely until the completion of the study.

12. Study Intervention

This study meets the criteria of a clinical trial but it is not a NIH-Defined Phase III Clinical Trial as defined by NIH. The UAB IDS pharmacy is responsible for the preparation and labeling of allopurinol and the placebo. Participants will be asked to take 4 weeks of allopurinol or placebo, then will crossover to the other drug (after 2-4 week washout period) and take either allopurinol or placebo for an additional 4 weeks. Allopurinol will be prescribed in 300mg tablets. At visit 2 and 4, participants will be given a 5-week (with an additional 7 days to account for variability in appt availability) supply of medication. During visits 3 and 5 study staff will count pills (any extra will be discarded) to determine compliance. Allopurinol and placebo prescriptions will be administered by the research study coordinator conducting the visit, daily doses will be administered by the participants themselves.

13. Participant Evaluations- Study timeline, visits, and procedures (See Protocol, Section F, for details on the study timeline, visit schedules, and procedures)

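### A repeated closing ambulatory BP recording is likely to be made after dosing has stopped, a minor bias toward no effect that a dosing instruction would remove

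*Combined protocol and SAP*

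**What the plan says.** The ABPM part of Section F defines a compliant recording as at least 14 daytime and 5 nighttime readings. For recordings below that: "Those with less than these minimal thresholds will be asked to repeat the test". If no compliant recording can be obtained, the value is multiply imputed. On the start of recording: "The first measurement will be obtained at the end of the clinic visit to ensure proper fit and function".

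The opening visits have a safeguard. The Visit 2 and Visit 4 lists both end with: "Dispense 4 week course of allopurinol or placebo based on treatment assignment following return of the ABPM monitor". The first opening recording is therefore free of the new phase's drug.

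At the closing visits the sequence differs. Section 12: "During visits 3 and 5 study staff will count pills (any extra will be discarded) to determine compliance". Section F, after the Visit 3 list: "Following Visit 3, participants will begin a “wash-out period” before crossing over to the alternate treatment assignment". Section 12 also gives a margin of supply at Visits 2 and 4: "participants will be given a 5-week (with an additional 7 days to account for variability in appt availability) supply of medication".

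The ABPM procedure in Appendix 3 (D) covers cuff fit and movement but not study drug. Table 3 gives no window for a repeat.

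**The concern.** Aim 1a in Section H compares the within-phase change in weighted 24-hour SBP and DBP between the allopurinol and placebo phases. A closing value taken after dosing has stopped misses part of any drug effect in the allopurinol phase and misses nothing in the placebo phase. An opening value taken on drug lowers the allopurinol baseline and works in the same direction. Neither the crossover nor the blinding cancels this, since both errors pull the allopurinol-minus-placebo difference toward zero.

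Section F lists ambulatory BP as a secondary outcome and the sample size rests on hsCRP. Ambulatory BP nevertheless carries Hypotheses 1 and 2 and the BP part of Aim 2. For Hypothesis 2, unequal repeat rates by race could add to or mask a difference. For Aim 2, a repeat BP would be paired with a urate value drawn earlier, at the visit. Urate, hsCRP and FMD themselves are collected at the visit and are not affected.

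**Working it through.** **1. Order of events at a closing visit.** The monitor starts at the end of the visit and runs 24 hours, so a shortfall is normally known about a day later. By then, on the plain reading, the spare pills are gone and (after Visit 3) washout has begun. A repeat starts at least 24 hours after the first recording began.

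**2. Drug exposure during a closing repeat.** Input from Section F: "Allopurinol has a half-life of 1-2 hours before being converted to oxypurinol, which has a half-life of 18 to 30 hours". Dose times and delays are assumptions. With k = ln 2 / half-life and once-daily steady state, mean exposure over a 24-hour recording starting s hours after the last dose, relative to a normal dosing day, is exp(-k·s).

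| Start after last dose | Half-life 18 h | Half-life 30 h |
|---|---|---|
| 2 h (first recording, dose taken that morning) | 93% | 95% |
| 26 h (next-day repeat: 2 + 24) | 37% | 55% |
| 72 h | 6% | 19% |
| 168 h | 0.2% | 2% |

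The first closing recording is essentially on drug if that morning's dose was taken. The problem lies with the repeat.

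**3. Drug exposure during an opening repeat**, if dosing has begun: 1 - exp(-24·n·k) on dosing day n. Day 1: 60% (18 h) or 43% (30 h) of steady state. Day 3: 94% or 81%.

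**4. How often a repeat is needed.** Scheduled readings: day 16 h × 3 = 48, night 8 h × 2 = 16. Failure means at most 13 day readings (35/48 = 73% lost) or at most 4 night readings (12/16 = 75% lost). The plan gives no failure rate.

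**5. The plan's SBP figure.** It states 90% power for 3.7 mmHg. With its SD of 8.5 mmHg and correlation of 0.10, the SD of the difference is 8.5 × √1.8 = 11.40. The detectable difference, (1.960 + 1.282) × 11.40/√N, is 3.83 mmHg at N = 93 and 3.49 at N = 112. No N is stated for SBP, and 3.7 fits about N = 100. This does not affect the present point, and the 90% is taken as given below.

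**6. What-if for BP (not an estimate).** If a share f of participants has an affected allopurinol-phase change and a share L of the effect is lost in it, the contrast is multiplied by (1 - f·L). Power = Φ(3.242 × (1 - f·L) - 1.960), variance unchanged. For a next-day closing repeat, suppose BP effect were proportional to exposure, so L = 1 - 0.55 = 0.45 to 1 - 0.37 = 0.63.

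| f (assumed) | L | SBP lost, of 3.7 mmHg | Power |
|---|---|---|---|
| 5% | 0.45-0.63 | 0.08-0.12 | 89-88% |
| 10% | 0.45-0.63 | 0.17-0.23 | 87-86% |
| 20% | 0.45-0.63 | 0.33-0.47 | 84-81% |
| 20% | 1.00 (extreme) | 0.74 | 74% |

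**7. Race comparison.** Repeat rates of 5% versus 20% with full loss: 3.7 × (0.20 - 0.05) = 0.56 mmHg, against the 5.8 mmHg that the plan can detect.

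**The case against.** The strongest reply is that a visit may stay open until its recording is complete. The Visit 2 and 4 lists include a step after monitor return, and Section E pays participants once a visit's procedures are finished. On that reading the discard and the start of washout could both come after a repeat. This is possible, but the text does not say so, and staff following Section 12 literally would discard the pills on the clinic day.

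Second, relevant text may be unavailable. The Section F sentence on mistimed recordings, which sends them to two blinded analysts, breaks off in the copy reviewed, and the participant ABPM instructions mentioned in Appendix 3 (A) are not reproduced. So it can be said only that no rule is visible. Even so, later review cannot restore drug exposure, and the visit forms shown in Appendix 2 have no field for last dose time. Oxypurinol levels with the recorded draw time describe the visit, not the days after it.

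Third, an opening repeat falls on drug only if staff dispense without checking the download. They could check first, and nothing forbids it. This makes it the lesser risk.

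A reader might infer that closing BP is generally measured off drug, or that the BP analysis is seriously underpowered as a result. The documents support neither. The first closing recording keeps about 93-95% of normal exposure after a morning dose, although no visible instruction asks for that dose. A next-day repeat still has a third to a half or more of normal exposure. The 74% power figure needs an assumed 20% repeat rate together with complete loss of effect.

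**Conclusion.** The concern holds as a minor one. On the plain reading of the visible text, a repeated closing recording is likely to be made after dosing has stopped, and any resulting bias in the allopurinol-minus-placebo BP change is toward no effect. An opening repeat on drug is a lesser risk in the same direction.

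The size cannot be derived from the documents: the repeat rate, the delay and the time course of BP after stopping are not given, and BP need not follow drug level hour by hour. For next-day closing repeats in 5-10% of participants, with effect proportional to exposure, the loss is 0.08-0.23 mmHg of 3.7 and one to four points of power. Repeats require loss of about three quarters of the day or night readings and may be uncommon. The conclusion assumes that no dosing rule stands in the cut-off sentence or in the participant instructions. If one does, the remedy is to state it in the protocol.

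**What to change.** Extend the opening-visit safeguard to the closing recording and to repeats:

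- Participants take study drug daily, including the visit day, until a compliant closing recording has been downloaded.
- The Visit 3 and 5 pill count and discard move to that point. The 7 spare days in Section 12 cover the extra doses. Section F speaks of a 4-week course, so the quantity dispensed should be confirmed.
- Washout is counted from the last dose.
- At Visits 2 and 4, staff check the download for compliance before dispensing, where the visit window allows.
- The date and time of the last dose are recorded. Closing repeats taken off drug and opening repeats taken on drug are flagged, and a sensitivity analysis omits them.

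The cost is protocol wording, one form entry and a later pill count. A phase or washout may shift by one to a few days. If Visit 4 did not move, three extra dosing days would cut a 14-day washout to 11, and residual oxypurinol, exp(-24·d·k) at the 30-hour half-life, would rise from 0.04% to 0.22%. For women, "Women will need to be evaluated between days 1-7 of their menstrual cycles for study visits", so holding the drug for one to three days could shorten a 28-day phase by 4-11% (1/28 to 3/28) if Visit 3 cannot move. That rule is there for FMD, which is done at the visit, so a closing BP repeat a few days later does not break it.
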